#### 3.5.7.2. Statistical analysis

Statistical analyses will be performed using either the R programming language and statistical environment (R Core Team, 2017) or IBM SPSS 27. Potential missing data will be replaced using multiple imputation (in SPSS).

Data for hearing aid users and cochlear implant users will be analysed separately. Potential relations between outcomes will be determined in a within-subject design, i.e., baseline session outcomes will be compared to the final session outcomes, with a repeated measures ANOVA ( $\alpha = 0.05$ ). We will correct for multiple comparisons using Dunn post-hoc tests with Holm correction (Dunn, 1961).

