#### Hypotheses on the clinical performance & effectiveness of the ALICE app

##### User-oriented outcomes for experienced HA/CI users

After 8 weeks of continued use of the ALICE-Client app persons with HI will:

- Indicate enhancement in their daily life listening and/or communication strategies (primary)
  - Enhanced speech understanding in difficult listening situations
  - Reduced listening effort
- Indicate to be more knowledgeable about their HI and recognize the emotional consequences of their HI (secondary)
- Indicate to be more satisfied with the delivered care and/or their hearing aid/cochlear implant in daily life (secondary).

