### 3.5.6.2. Research ARM 1 (approved by EC on 25/08/2022 – ref. CIV-22-06-039801)

**Description of the design type of clinical investigation to be performed (e.g. comparative double-blind, parallel design, with or without a comparator group) with rationale for the choice**

The study design is a randomized controlled clinical trial (RCT) which is the golden standard for ascertaining the efficacy and safety of a new treatment or intervention. The goal of the current RCT is to demonstrate the superiority of the ALICE app, as a new intervention over the existing standard of care.

In this RCT two groups will be compared:

- (1) A group that receives the standard of care, which is defined as followed:
  - a. Persons with a moderate to profound HI who are provided with a hearing aid
  - b. Persons with a profound to severe HI who are provided with a cochlear implant and concomitant rehabilitation. Most persons with a cochlear implant receive intensive rehabilitation during the first 6 months after their implantation. Afterwards, they mainly return for mapping of the device but not for listening training therapy.
- (2) A group that receives the standard of care, supplemented with the ALICE app, to be used as a home-based monitoring, training and counselling tool.

Description of the measures to be taken to minimize or avoid bias, including randomization, concealment of allocation, blinding/masking, assessment of blinding plan and management of potential confounding factors

For each investigator site clients will be recruited by the local principal investigator (PI) of the study (HCPs working in the hearing centre or university hospital). Once the HCP has recruited the required number of clients, they will send the list of clients to the KU Leuven researcher who will divide the clients randomly across the two groups (standard of care/additional use of ALICE). Randomisations of these two groups will be stratified according to age and will be done automatically with an automatic seed generator.

We foresee a few possible confounding factors:

- Medical confounding factors
  - o Type and degree of HI
  - o Comorbidities such as high blood pressure, diabetes, stroke, visual acuity, cognitive abilities
- Methodological confounding factors

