*Description of all the clinical-investigation-related procedures that subjects undergo during the clinical investigation including any deviation from normal clinical practice*

Below, the timeline of the test protocol is presented: After allocation to a treatment group, a client will be assessed with speech in noise and questionnaires (Figure 4), followed by 8 weeks use of the ALICE app. The same outcome measures will be assessed at the final appointment to evaluate the benefit of the intervention.

[figure not shown]

Figure 4. Timeline of the test protocol.

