#### Description of the design type of clinical investigation to be performed (e.g. comparative double-blind, parallel design, with or without a comparator group) with rationale for the choice

The study design is a randomized controlled clinical trial (RCT) which is the golden standard for ascertaining the efficacy and safety of a new treatment or intervention. The goal of the current RCT is to demonstrate the superiority of the supplementary use of the ALICE app, as a new intervention over the existing standard of care.

In this RCT two groups will be compared:

- (1) A group that receives the standard of care, which is defined as followed:
  - a. Persons with a moderate to profound HI who are provided with a hearing aid
- (2) A group that receives the standard of care, supplemented with the ALICE app, to be used as a home-based monitoring, training and counselling tool.

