    - Procedure to follow in case of adverse events and/or device malfunction
  - Rights and responsibilities
- Installation of the app
  - Intended use of the app
  - Compatibility of the app with personal (streaming) devices,
  - Instruction to use the app
  - First installation and set-up of account
- Test protocol (see below and Fig. 4)

*Description of all the clinical-investigation-related procedures that subjects undergo during the clinical investigation including any deviation from normal clinical practice*

Below, the timeline of the test protocol is presented after allocation to a treatment group a client will be assessed with speech in noise and questionnaires (Figure 5). Followed by 4 to 6 weeks use of the ALICE app. The same outcome measures will be assessed at the end of the hearing aid trial period to evaluate the benefit of the intervention.

[figure not shown]

Figure 5. Timeline of the test protocol of the second research arm

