### 3.5.6.4. Research ARM 3 (NEW!)

The main goal of the third arm of the clinical study is to evaluate the performance (and viability) of the French version of the ALICE app. This arm will be carried out in 8 hearing aid centres geographically spread across the French-speaking part of Belgium (the Walloon Region and Brussels). The duration of the study is estimated around 9 months (see procedures for the overview of the time line).

**Description of the design type of clinical investigation to be performed (e.g. comparative double-blind, parallel design, with or without a comparator group) with rationale for the choice**

The study design is a randomized controlled clinical trial (RCT), which is the golden standard for ascertaining the efficacy and safety of a new treatment or intervention. The goal of the current RCT is to demonstrate the superiority of the supplementary use of the ALICE app, as a new intervention, over the existing standard of care.

In this RCT two groups will be compared:

- (1) A group that receives the standard of care, which is defined as followed:
  - a. Persons with a moderate to profound HI who are provided with a hearing aid
- (2) A group that receives the standard of care, supplemented with the French version of the ALICE app, to be used as a home-based monitoring, training and counselling tool.

**Description of the measures to be taken to minimize or avoid bias, including randomization, concealment of allocation, blinding/masking, assessment of blinding plan and management of potential confounding factors**

For each investigator site, clients will be recruited by the local study team (HCPs working in the hearing centre). Once the HCP has recruited the required number of clients, they will send the list of clients to the KU Leuven researcher, who will then divide the clients randomly across the two groups (standard of care/additional use of French ALICE). Randomisation of these two groups will be stratified according to age with an automatic seed generator.

We foresee a few possible confounding factors:

- Medical confounding factors
  - Type and degree of HI
  - Comorbidities such as high blood pressure, diabetes, stroke, visual acuity, cognitive abilities
- Methodological confounding factors
  - Potential procedural effects for the questionnaires may occur and will be controlled for by administering the questionnaires twice prior to the participants starting the training and at the end of the 8 week training period

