### 3.5.7. Statistical design and analysis

#### 3.5.7.1. Sample size

HCPs from the hearing centres participating in the first, second and third arm of the study will include a total of 390 hearing aid users (150 in the first arm, 120 in the second arm and 120 in the third arm). HCPs from UZ Leuven will include 30 CI users for the first arm only. Clients will be equally divided among participating investigation sites. After being stratified by age, they will be randomly assigned to two groups of approximately 195 hearing aid users (75 in the first arm, 60 in the second arm and 60 in the third arm), and two groups of 15 CI users (first arm only). One group will receive the standard of care, the other group will receive the standard of care supplemented with the ALICE app (The Dutch version in both the first and second arm the French version in the third arm).

Scientific literature was consulted to estimate the group size needed for our RCT and a power analysis was conducted to confirm the effect size for this sample.

Power analysis conducted with the G\*Power software (Erdfelder et al., 2009) indicated that a total sample of at least 76 persons is needed to detect differences in speech understanding in noise outcomes between the two treatment groups with a low to medium effect size ( $d = 0.25$ ) to have statistical power of 95% using a repeated measures ANOVA ( $\alpha = 0.05$ ). We will be able to recruit more clients via the hearing centers (between 15 and 30 persons per hearing center). We estimate that, for all three arms of the study, 390 persons with a HA will take part in the trial and, for the first arm of the study only, about 30 persons with a CI. This larger number accounts for clients being lost to follow-up during the study.

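### The analysis section describes a before–after comparison and never states the contrast between randomised groups that the superiority aim needs

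*Combined protocol and SAP*

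**What the plan says.** The aim is comparative in every arm. Section 3.5.6.2 (Arm 1) sets out to "demonstrate the superiority of the ALICE app, as a new intervention over the existing standard of care", section 3.5.6.3 (Arm 2) to "demonstrate the superiority of the supplementary use of the ALICE app, as a new intervention over the existing standard of care" and section 3.5.6.4 (Arm 3) to "demonstrate the superiority of the supplementary use of the ALICE app, as a new intervention, over the existing standard of care". All three randomise to two groups and say these will be compared. Section 3.5.7.1 bases its total of 76 on the number "needed to detect differences in speech understanding in noise outcomes between the two treatment groups", using a repeated measures ANOVA.

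Section 3.5.7.2 is the only description of the analysis. It says: "Potential relations between outcomes will be determined in a within-subject design, i.e., baseline session outcomes will be compared to the final session outcomes", again by repeated measures ANOVA at alpha 0.05. The one split it names is hearing-aid users versus cochlear implant (CI) users, which is not randomised. The Dunn/Holm sentence does not say which comparisons it covers.

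Elsewhere the wording leans the same way. The Arm 1 and Arm 3 test protocols say: "The same outcome measures will be assessed at the final appointment to evaluate the benefit of the intervention". Arm 2 says: "The same outcome measures will be assessed at the end of the hearing aid trial period to evaluate the benefit of the intervention". The hypotheses for experienced users in section 3.5.5.1 open with "After 8 weeks of continued use of the ALICE-Client app persons with HI will" and name no comparator.

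**The concern.** A repeated measures ANOVA with two groups and two sessions yields a time effect, a group effect and a group-by-time interaction. Section 3.5.7.2 describes the first. Only a contrast between the randomised groups can show that the app adds something to standard of care, and no section states one.

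No sentence says that a change over time will be credited to the app. But it is the only comparison the analysis section writes down, and the test protocols tie the repeat assessment to the benefit of the intervention. The reader cannot tell which p-value decides efficacy, so it could be chosen after the results are known.

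The documents themselves foresee changes that both groups could share: procedural effects on the questionnaires (confounding-factor lists of all three arms) and, in Arm 2, habituation to a first hearing aid. The LIST sentence test in Arm 1 is least exposed, because section 3.5.6.2 expects little procedural effect there.

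The stated comparison also cannot be run on some Arm 2 secondary outcomes. Face-to-face time and the numbers of tests, fittings and appointments accrue during the hearing-aid trial and have no baseline. Daily hearing-aid use has no pre-trial value in first-time users.

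**Working it through.** **1. Does the stated sample size show which test was meant?** Inputs from section 3.5.7.1: effect 0.25, power 95%, alpha 0.05, total 76. Assumptions: 0.25 is read as Cohen's f, with two groups and two sessions. Section 3.5.7.1 labels the effect d and gives no correlation r.

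- Time effect and group-by-time: λ = f² × N × 2 / (1 − r).
- At N = 76 and r = 0.3: λ = 0.0625 × 76 × 2 / 0.7 = 13.6, on 1 and 74 degrees of freedom, power 95.3%. At N = 74 power is 94.8%. So 76 is reproduced at r of about 0.3, but r is not in the plan.
- The time effect and the interaction share this formula, so 76 cannot show which was used.
- The between-group main effect, averaged over sessions, needs 106 to 180 for r = 0 to 0.7, and never 76.

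**2. How often would the time effect be significant with no app effect?** Assumptions, since the documents give neither value: both groups shift by δ (in SDs of the outcome) and r = 0.3, 0.5, 0.7 or 0.8. Group sizes are from section 3.5.7.1: 150 hearing-aid users in Arm 1, 120 each in Arms 2 and 3, and 30 CI users. All participants are analysed together, because section 3.5.7.2 does not split by randomised group.

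Noncentrality = δ × √n / √(2(1 − r)), with n − 1 degrees of freedom. Example: n = 120, δ = 0.1, r = 0.5 gives 0.1 × 10.95 / 1 = 1.10, hence 19.1%.

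Probability of significance in the favourable direction (nominal 2.5%):

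| n | δ | r = 0.3 | 0.5 | 0.7 | 0.8 |
|---|---|---|---|---|---|
| 120 | 0.05 | 6.7% | 7.8% | 10.4% | 13.5% |
| 120 | 0.1 | 14.9% | 19.1% | 28.9% | 40.4% |
| 120 | 0.2 | 45.1% | 58.4% | 80.1% | 93.0% |
| 150 | 0.1 | 17.6% | 22.9% | 34.9% | 48.6% |
| 150 | 0.2 | 53.9% | 68.2% | 88.1% | 97.0% |
| 30 | 0.1 | 6.5% | 7.6% | 10.1% | 13.1% |
| 30 | 0.2 | 14.4% | 18.4% | 27.7% | 38.8% |

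At δ = 0 every entry is 2.5%.

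**3. Does a between-group test avoid this?** Simulation with no app effect: 10,000 trials per setting; 60, 75 or 15 per group; δ = 0, 0.1, 0.2; r = 0.3, 0.5, 0.8. Two-sided rejection was 4.7–5.5% for group-by-time and 4.5–5.3% for the baseline-adjusted comparison, against a nominal 5%.

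**4. Does it cost power?** Assume an app effect a = 0.5 SD, no shared shift and m = 60 per group.

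- Time effect over both groups: (a/2) × √(2m) / √(2(1 − r)).
- Group-by-time: a × √(m/2) / √(2(1 − r)).
- These are equal; at r = 0.5 both are 2.74. Power is 63%, 78%, 94% and 99% for r = 0.3, 0.5, 0.7 and 0.8 with either test.
- Variance of the baseline-adjusted contrast relative to change scores: (1 − r²) / (2(1 − r)) = (1 + r)/2, so 25% less at r = 0.5 and 15% less at r = 0.7.

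**The case against.** The strongest reply is that a group comparison is plainly intended. Section 3.5.7.1 links the same ANOVA to a between-group difference, every arm says two groups will be compared, and the Arm 2 hypothesis of faster habituation implies a comparator. The sentence in section 3.5.7.2 is also loosely worded: its subject is relations between outcomes, and it does not call itself the efficacy test. All of this is fair, and the defect is a contrast left unstated, not evidence that none will be run. But the sentence defines its comparison as baseline against final, and no other section names the term to be tested.

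The size of the inflation also depends on the reading. If the before–after test were run in the app group alone (n = 60), the rates fall to 9–23% at 0.1 SD and 25–67% at 0.2 SD. At the strictest Holm step over six outcomes (the instruments in Table 1), the pooled test with n = 120 gives 4–18% per outcome at 0.1 SD. Both remain above their nominal levels (2.5%, and 0.05/6/2 = 0.4%). Against an app-group-only test, group-by-time does have less power: 63% against 90% at 60 per group, r = 0.3 and 0.5 SD. That extra power comes from ignoring the control group. With 15 CI users per group, group-by-time power for 0.5 SD is only 20–55%.

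The plan says questionnaire procedural effects will be controlled by repeat administration. The wording is unclear, and even if it works it does not supply the missing contrast. Finally, the Arm 2 timing figure is not shown, so an early hearing-aid datalog reading cannot be ruled out. Face-to-face time and the appointment counts still have no baseline.

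**Conclusion.** The concern holds and should be corrected before analysis. As written, section 3.5.7.2 does not test the superiority aim of any arm or the difference powered in section 3.5.7.1. This conclusion rests on the text and needs no assumed number.

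The consequence depends on a shared shift and a correlation that the documents do not give. Under the literal reading, for r = 0.3 to 0.8, a shared shift of 0.1 to 0.2 SD would give a favourable significant result with no app effect in 15–93% of trials with 120 participants, 18–97% with 150 and 6.5–39% with 30.

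**What to change.** Add to section 3.5.7.2: *Within each arm, and separately for hearing-aid and CI users, the efficacy test for each outcome is the contrast between the randomised groups, with a 95% confidence interval. Outcomes without a baseline value are compared between groups at the end of the period. Baseline-to-final changes, within a group or over both groups, are descriptive only. Holm correction is applied to the between-group p-values.*

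Working within each arm fits the design, since each arm is its own randomised trial with its own speech test (LIST, BLU, Lafon). At minimum the contrast is the group-by-time term of the ANOVA already planned, which is valid. For precision only, I would prefer the final score compared between groups with adjustment for baseline score and age, the stratification factor. The sponsor should name one in advance and define the Holm family so that it respects the primary and secondary labels. Site adjustment is optional. Usability items of the ALICE questionnaire exist only for app users and stay descriptive.

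The cost is wording, with no new data collection. The change must be dated before group results are seen. Arm 1 was approved in August 2022 with a 12-week recruitment window, so its data may already exist. Under section 3.5.9 the sponsor must judge whether this is a substantial amendment, which would require submission to the competent authority and ethics committee approval.

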## 3.5.8. Data management

### 3.5.8.1. Data Collection Tools and Source Document Identification

#### Operational aspects

Data collection, handling, processing and transfer for the purpose of this Trial will be performed in compliance with applicable regulations, guidelines for clinical trials and internal procedures, as follows:

##### *Data collection*

**Source Data** will be collected and recorded in the Trial participant's files/medical records.

If applicable, worksheets may be used for capturing some specific data in order to facilitate completion of the (e)CRF. Any such worksheets will become part of the Trial participant's source documentation and will be filed together with or as part of the medical records (during but also following completion of the Trial).

It remains the responsibility of the Investigator to check that all data relating to the Trial, as specified in the Trial protocol (=CIP), are entered into the (e)CRF in accordance with the instructions provided and that the forms are filled out accurately, completely and in a timely manner.

(e)CRFs are provided by the Sponsor (here the coordinating investigator) for each participant. The Trial data will be transcribed from the source records (i.e. participant's medical file or Trial-specific source data worksheets) into an (e)CRF by Trial Staff (here the local PI). Transcription to the (e)CRF will be done as soon as possible after a participant visit and in a pseudonymized manner using a unique identifier assigned by the Sponsor.

The (e)CRFs will be available for review at the next scheduled monitoring visit (as applicable) and shall under no circumstances capture personal data such as but not limited to the participant or their relative(s) name, home address, contact details, full date of birth medical record number (e.g. UZ Leuven EAD number), social security number etc.

##### *Data Validation*

All data relating to the Trial must be prepared and validated by the local PI and coordinating Investigator. Any (e)CRF entries, corrections and alterations must be made by the PI or other authorized Trial staff.

Proper audit trails must be available to demonstrate the validity of the Trial data collected. This includes historical records of original data entries, by whom and when the data was entered, as well as detailed records of any corrections or additions made to the original data entry (i.e. who made the correction/addition, when and why), without obliterating the original data entry information.

##### *Data Management*

The Trial Data Manager (here coordinating investigator) will perform extensive consistency checks on the received data. Queries will be issued in case of inconsistencies in accordance with internal procedures. A Data Management Plan (DMP) will be developed to map data flows, data validation measures that will be taken, how (interim) database lock(s) will be managed and, as applicable, the role and responsibilities of the Data Safety Monitoring Committee (DSMB)

##### *Data Transfer*

Any participant records or datasets that are transferred to the Sponsor or any partners of the Sponsor will contain the Trial-specific participant identifier only; participant names or any information which would make the participant identifiable will not be transferred. All pseudonymized data relating to the Trial must be transmitted in a secure manner to the Sponsor or any partners of the Sponsor (see 8.1.2. legal requirements).

## Legal requirements

All source data will be kept at a secured location with restricted access at all times. These data must be collected and processed with adequate precautions to ensure confidentiality and compliance with applicable data protection laws and regulations and more in particular the EU General Data Protection Regulation 2016/679 (GDPR) and relevant national laws implementing the GDPR. Appropriate technical and organizational measures to protect the data against unauthorized disclosure or access, accidental or unlawful destruction, or accidental loss or alteration must be established. Trial staff whose responsibilities require access to personal data agree to keep the data confidential.

The Investigator and the Participating Site(s) (as applicable) shall treat all information and data relating to the Trial disclosed to them as confidential and shall not disclose such information to any third parties or use such information for any purpose other than the objectives of the Trial as described in this protocol. The collection, processing and disclosure of personal data, such as participant health and medical information is subject to compliance with applicable laws and regulations regarding personal data protection and the processing of personal data.

The Investigator will maintain all source documents and completed (e)CRFs that support the data collected from each Trial participant, and will maintain a Trial Master File (TMF)/Investigator Site File (ISF) containing all Trial documents as specified in ICH-GCP E6(R2) Chapter 8 entitled "Essential Documents for the Conduct of a Clinical Trial", and as specified by applicable regulatory requirement(s).

The Investigator will take appropriate measures to prevent accidental or premature destruction of these documents.

Transfer of the pseudonymized data will be performed via a secured method of transfer taking into account all applicable security arrangements and regulations (such as the European General Data Protection Regulation). The receiving party will be bound by contractual agreement to keep the transferred data confidential at all times and to only process the data for the purpose of the Trial. To this end, appropriate Data Transfer Agreements (DTAs) will be established.

